#### **5.1.1.4 Patient Global Impression of Change (PGIC)**

The PGIC is a global measure indicating the degree of change in SCD related pain compared to the start of treatment, as evaluated by the patient. Patients will be asked to evaluate “Since

the start of the treatment I have received in this study, my sickle cell pain is” and response options are a 7-point Likert response scale with the following categories: Very much improved; Much improved; Minimally improved; No change; Minimally worse; Much worse and; Very much worse ([Dworkin et al 2005](#)).

The patient will be asked to fill in the PGIC at end of treatment in the eDiary.

### **5.1.2 Vaso-occlusive crisis (VOC)**

At each visit, patients will be questioned regarding any painful sickle cell crises occurring. For each event, the Investigator will complete necessary information in the eCRF. VOC is defined as a composite endpoint of painful sickle cell crisis or acute chest syndrome. Acute chest syndrome is defined as an acute illness characterized by fever and/or respiratory symptoms, accompanied by a new pulmonary infiltrate on a chest X-ray. A painful sickle cell crisis is defined as an onset of moderate to severe pain (that has no other explanation than VOC) that lasts at least 2 hours and requires medical intervention including oral or parenteral opioids or parenteral NSAIDs in any of the following settings:

- In-patient hospitalisation
- Emergency department
- Short-stay outpatient unit
- Medical clinic outpatient
- Medically supervised outpatient treatment with escalated pain medication (e.g. management by telephone)
- Self-treated (no consultation with medical personnel prior to escalation of pain medication)

The occurrence of a VOC event is considered an efficacy event of the disease under study primarily reported on the eCRF VOC module and should not be recorded as an AE. If a VOC event fulfils any criteria of an SAE according to the definition (see [Appendix B](#)) or result in discontinuation of IP, it should be reported both on the eCRF VOC module and as an SAE or AE respectively. See Section [6.3](#).

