## 1.4 Study Design

This study includes 3 periods Screening, Treatment and Follow-up. **Screening** period starts from enrolment (Visit 1) and patients will receive total 4-weeks (Day -28 to Day 0), single-blind double-dummy placebo treatment bid to determine the frequency and intensity of days with pain at baseline using a daily electronic diary (eDiary). Patients with  $\geq 4$  days of pain during the Screening period will be eligible for randomisation. **Treatment** period starts from randomisation (Visit 2) and then patients will receive total 12 weeks of double-blind double-dummy treatment bid until end of treatment (Visit 5). Patients may be asked to participate in a voluntary collection of biomarkers for exploratory analysis. **Follow-up** period starts after end of treatment and patients will be followed for safety assessment after 2 weeks (Visit 6, telephonic contact). During the study, patients will be evaluated for adverse events (AEs) including bleeding and VOC.

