#### 4. STUDY PLAN AND TIMING OF PROCEDURES

**Table 1 Study Plan Detailing the Procedures**

Study Period	Screening period	Treatment period				Follow-up period	For details see Protocol Section
Visit	Enrolment	Randomisation	Treat-ment	Treat-ment	End of treatment	Phone contact	
Visit Number	1	2	3	4 a	5	6	
Week	-4	0	1	4	12	14	
Day	-28	0	7	28	84	98	
Visit Window	-35 to -28	Not Applicable	±3 days	±7 days	±7 days	±7 days	
Signed and Dated Informed consent	✓						10.4
Inclusion/Exclusion Criteria	✓	✓ b					3.1 and 3.2
Allocation of E-code via IVRS/IWRS	✓						3.3
Randomisation via IVRS/IWRS		✓					3.3 and 3.5
Electronic Diary Assessment c : – Pain (worst/ average/ right now), daily – Analgesic use, daily – Absence school/ work, weekly – PGIC, end of treatment							5.1.1
Medical and Surgical History	✓						4.1
Demographics	✓						4.1
Vital Signs (BP and Pulse Rate)	✓	✓	✓	✓	✓		5.2.4
Weight and Height	✓				✓ d		5.2.4
Physical Examination	✓				✓		5.2.2
12-Lead ECG	✓						5.2.3
Ophthalmology examination (if not performed within previous 12 months)	✓						4.1

Study Period	Screening period	Treatment period				Follow-up period	For details see Protocol Section
Visit	Enrolment	Rando-misation	Treat-ment	Treat-ment	End of treatment	Phone contact	
Visit Number	1	2	3	4 a	5	6	
Week	-4	0	1	4	12	14	
Day	-28	0	7	28	84	98	
Visit Window	-35 to -28	Not Applicable	±3 days	±7 days	±7 days	±7 days	
Blood samples for Hematology and Clinical Chemistry	✓			✓	✓		5.2.1
Blood samples for coagulation (INR and PTT)	✓						5.2.1
Virology screen (HIV, HBsAg, and HCV)	✓						5.2.1
Urinalysis (dipstick)	✓			✓	✓		5.2.1
Pregnancy Test e	✓	✓		✓	✓		5.2.1
Platelet aggregation (PRU) (VerifyNow) f		✓	✓				5.5.1
Blood sampling for Biomarkers (optional)		✓ g	✓	✓			5.7
Blood sampling for Pharmacokinetics h		✓	✓				5.4
Dispense IP	✓ i	✓		✓			7
Administration of IP in Clinic	✓ i	✓	✓				7
Return IP and Drug Accountability		✓		✓	✓		7.5 and 7.6
Vaso-occlusive crisis	✓ j	✓	✓	✓	✓		5.1.2
Concomitant Medications	✓	✓	✓	✓	✓	✓	7.7
Adverse Event review (AEs and SAEs) including bleeding events	✓	✓	✓	✓	✓	✓	6

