#### **4.2.4 Visit 5, End of treatment visit**

- Patient eDiary will be collected
- Review concomitant medications and AEs including bleeding events
- Obtain vital signs (pulse rate and BP), body weight
- Perform standard physical examination
- Obtain specimens (blood) for safety laboratory panel
- Obtain specimen for urinalysis and perform urine pregnancy test for females of child bearing potential
- Collect and assess compliance with study drug based on tablet count

Instruct the patient that they will be contacted for safety assessment through telephone after 2 weeks.

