#### **4.3        **Follow-up period****

Visit 6 is safety follow-up visit, during which all patients will be contacted by telephone by site personal to check their concomitant medications and for any AEs including bleeding events.

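### The protocol contradicts itself on whether vaso-occlusive crises are asked about and recorded at the Visit 6 follow-up call

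*Protocol*

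**What the plan says.** Two parts of the protocol point towards asking about VOC at Visit 6:

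- Section 5.1.2: "At each visit, patients will be questioned regarding any painful sickle cell crises occurring". No visit is excepted, and the investigator is to complete the eCRF for each event. Section 4.3 counts the telephone contact as a visit: "Visit 6 is safety follow-up visit".
- Section 1.4, directly after describing the follow-up period: "During the study, patients will be evaluated for adverse events (AEs) including bleeding and VOC".

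Two parts point the other way:

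- Table 1: the row "Vaso-occlusive crisis" is ticked at Visits 1 to 5 and blank at Visit 6. The rows for concomitant medication and adverse events are ticked at all six visits.
- Section 4.3: at Visit 6 patients are "contacted by telephone by site personal to check their concomitant medications and for any AEs including bleeding events". VOC is not named.

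Two further rules decide what follows if VOC is not asked about. Section 5.1.2 says a VOC is "primarily reported on the eCRF VOC module and should not be recorded as an AE", except when it meets a seriousness criterion or leads to discontinuation of study drug. Section 4.2.4 lists, at Visit 5, "Patient eDiary will be collected", so daily pain reporting ends with treatment.

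**The concern.** Taking VOC out of adverse event reporting works only while the VOC module is in active use. Section 6.3.1 runs adverse event collection to Visit 6, so the exclusion runs to Visit 6 too. In Table 1, the scheduled VOC question that takes its place stops at Visit 5.

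The purpose of the follow-up is stated in Section 1.4: "patients will be followed for safety assessment after 2 weeks (Visit 6, telephonic contact". Section 6.1 defines an adverse event to include deterioration of an existing condition after exposure. A crisis in the weeks after treatment would therefore normally count as one; only the VOC rule removes it. If sites resolve the conflict differently, the VOC count for this period depends partly on which section each site followed. It could then not be summarised meaningfully.

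**Working it through.** The protocol gives no figure to reproduce here. The check sets its instructions side by side and follows a non-serious crisis that begins after Visit 5.

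| Route by which the crisis could be recorded | Source | Available after Visit 5? |
|---|---|---|
| Scheduled VOC question, by the text | Sections 5.1.2 and 1.4 | Yes: every visit, and Visit 6 is called a visit |
| Scheduled VOC question, by the schedule | Table 1 | No: blank at Visit 6 |
| Content of the call | Section 4.3 | Not named |
| Adverse event form | Section 5.1.2 | Barred unless serious; the drug-discontinuation exception cannot apply once treatment is complete |
| Serious adverse event report | Sections 5.1.2, 6.2 and 6.3.1 | Only if a seriousness criterion is met |
| eDiary | Section 4.2.4 | No: handed back at Visit 5 |
| Concomitant medication | Table 1, Sections 4.3 and 7.7.2 | Yes, as a medication entry, not as a VOC |
| Information reaching the investigator in routine care | Section 5.1 | Yes, but unsystematic |

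**What falls in the gap.** The VOC definition in Section 5.1.2 includes crises handled in the emergency department, in clinic, by telephone or by the patient alone. Appendix B states that outpatient emergency-room treatment is not serious in itself. Several settings that qualify as VOC therefore need not produce a serious adverse event report.

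**Length of the period.** Table 1 puts Visit 5 at Day 84 and Visit 6 at Day 98.

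- 98 − 84 = 14 days
- 14 / 98 = 14.3% of nominal time after randomisation
- 90 patients × 14 days = 1,260 patient-days; 1,260 / 365.25 = 3.45 patient-years, if all 90 reach both contacts

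Both visits carry a window of ±7 days. If both windows are counted from randomisation, the interval for one patient can run from 91 − 91 = 0 days to 105 − 77 = 28 days, so 14 days is nominal.

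**Number of crises.** The protocol gives no VOC rate and no non-serious share, so the number of events at risk of being missed cannot be estimated from it.

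**The case against.** The strongest reply is that the protocol already requires the question. Section 5.1.2 covers each visit, Section 4.3 calls the call a visit, and Section 5.2.4 spells out an exception for Visit 6 when vital signs are to be skipped. Section 4.3's silence is weak evidence too, because the lists for Visits 2 to 5 in Section 4.2 also omit VOC. The open health question in Section 6.3.5 may bring a crisis to light, and the VOC module exists to receive it.

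Most of this stands. It shows that the protocol does not forbid recording. It does not explain Table 1, where VOC is ticked at five visits and left blank only at Visit 6, next to two rows ticked at all six. No passage says which instruction prevails.

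A reader might go further and infer that non-serious crises after treatment have no place in the database, or that worsening after stopping drug would be invisible. The documents do not support either reading. The VOC module is the place, and Section 5.1.2 read literally sends the event there. Crises that meet seriousness criteria, including every in-patient admission, are reported up to Visit 6. A painful crisis by definition needs opioids or parenteral NSAIDs, so it should leave a dated medication entry with its indication. Such an entry is a trace, though, not an event judged against the VOC definition.

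A reader might also infer that a planned safety conclusion is undermined. No objective concerns worsening after withdrawal. The safety objective in Section 2.3 covers bleeding, adverse events, vital signs and laboratory samples, and VOC frequency is exploratory under Section 2.4.

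**Conclusion.** The contradiction is real and the point is minor. Sections 5.1.2 and 1.4 imply that VOC is asked about at Visit 6; Table 1 leaves it out and Section 4.3 does not name it. Sites that follow Table 1 would not systematically record non-serious crises in the follow-up, while sites that follow Section 5.1.2 would. VOC counts for that period would be incomplete and not comparable between sites.

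The effect is confined to non-serious crises between Visit 5 and Visit 6, nominally 14 days per patient. On-treatment VOC frequency is not affected, and neither is the primary endpoint. The conclusion rests on the text and schedule alone and assumes only that sites may differ in which instruction they follow.

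**What to change.** Reconcile Sections 1.4, 4.3, 5.1.2 and Table 1:

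1. Tick the VOC row at Visit 6 in Table 1.
2. Add to the call content in Section 4.3: *and any VOC since Visit 5 (VOC eCRF module)*.
3. Have the statistical analysis plan summarise these events by arm, separately from on-treatment VOC, so that they do not enter the exploratory frequency endpoint.

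The cost is one question on a call that already takes place and one more use of an existing eCRF module. No visit, sample or procedure is added, and nothing in the treatment or management of patients changes.

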## **5.2 Safety assessments**

### **5.2.1 Laboratory safety assessments**

Blood and urine samples for determination of clinical chemistry, haematology, virology (only at Visit 1), coagulation (only at Visit 1), and urinalysis will be taken at the times indicated in the Study Plan (see Section [4](#)). Additional safety samples for central lab assessment may be collected during unscheduled visits if clinically indicated at the discretion of the Investigator. The date, time of collection and results (values, units and reference ranges) will be recorded on the appropriate eCRF module.

The clinical chemistry, haematology, virology and coagulation will be performed at a central laboratory. Sample tubes and sample sizes may vary depending on laboratory method used and routine practice at the site but it is crucial that the blood volume is not exceeding the volume stated in [Table 3](#).

Urinalysis is to be performed at the investigational site by dipstick. A serum pregnancy test ( $\beta$ -hCG) will be taken at Visit 1 and a urine pregnancy test will be taken at Visit 2, Visit 4 and Visit 5 in females of child bearing potential. If female patients achieve menarche during the study, a urine pregnancy test should be performed before any study procedures at the next visit. The following laboratory variables will be measured:

**Table 2 Laboratory Safety Variables**

Haematology/Haemostasis (whole blood)	Clinical Chemistry (serum)
B-Haemoglobin (Hb)	S-Creatinine
B-Haematocrit	S-Bilirubin, total
B-Leukocyte count	S-Bilirubin, direct
B-Leukocyte differential count (absolute count)	S-Alkaline phosphatase (ALP)
B-Platelet count	S-Aspartate transaminase (AST)
	S-Alanine transaminase (ALT)
Urinalysis (dipstick)	S-Lactate dehydrogenase (LDH)
U-Hb/Erythrocytes/Blood	S-Uric Acid
U-Protein/Albumin	S-Blood Urea Nitrogen (BUN)
U-Glucose	S-Albumin
U-beta-human chorionic gonadotropin ( $\beta$ -hCG)	S-Potassium
	S-Chloride
Virology Screena	S-Sodium
Hepatitis B surface antigen (HBsAg)	S-Glucose
Hepatitis C virus (HCV)	S-Carbon Dioxide
HIV	S-Haptoglobin
	S- $\beta$ -hCG (Screening only)
	Coagulationa
	International normalized ratio (INR)
	Partial Thromboplastin Time (PTT)

a Virology screen and coagulation will be conducted at the Screening Visit only.  
Prefix: B for blood; S for serum; U for urine.

The Investigator should make an assessment of the available results with regard to clinically relevant abnormalities. The laboratory results should be signed and dated and retained at centre as source data for laboratory variables. For information on how AEs based on laboratory tests should be recorded and reported, see Section 6.3.

**NB.** In case a patient shows an AST **or** ALT  $\geq 3 \times \text{ULN}$  **or** total bilirubin  $\geq 2 \times \text{ULN}$  please refer to [Appendix D](#) ‘Actions required in cases of combined increase of Aminotransferase and Total Bilirubin – Hy’s Law’, for further instructions.

### **5.2.2 Physical examination**

A complete physical examination will be performed at enrolment (Visit 1) and at the end of treatment visit (Visit 5) and include an assessment of the following: general appearance, respiratory, cardiovascular, abdomen, skin, head and neck (including ears, eyes, nose and throat), lymph nodes, thyroid, musculo-skeletal (including spine and extremities) and neurological systems.

### **5.2.3 ECG**

#### **5.2.3.1 Resting 12-lead ECG**

A 12-lead ECG (standard ECG with a paper speed of 25 or 50 mm/second covering at least 6 sequential beats) will be recorded at enrolment (Visit 1) after the patient has been lying down to rest for up to 5 minutes. After paper ECG has been recorded, the Investigator or designated physician will review each of the ECGs for patient eligibility and entered as ‘Normal’ or ‘Abnormal’ in the eCRF. If the ECG is evaluated as “Abnormal” the Investigator should document the specific abnormality. Follow-up ECG will be performed during study only if clinically indicated. A standardised ECG machine should be used and a paper copy of ECG tracing should be filed in the patient’s medical records.

### **5.2.4 Vital signs**

#### **Blood pressure and pulse rate**

Pulse rate and systolic and diastolic blood pressure (BP) will be assessed using non-invasive equipment after the patient has been sitting at rest for 5 minutes. Results will be recorded in the eCRF. Pulse rate and BP will be measured at every visit (except Visit 6).

#### **Weight and Height**

Weight and Height assessments will be performed at the visits as shown in [Table 1](#). Results will be recorded in the eCRF.

### **5.3 Other assessments (Not Applicable)**

### **5.4 Pharmacokinetics**

#### **5.4.1 Collection of samples**

Blood samples for determination of ticagrelor and its active metabolite in plasma will be taken at the times presented in the study plan [Table 1](#). The actual date and time will be collected in the eCRF.

Samples will be collected, labelled stored and shipped as detailed in the Laboratory Manual. A central laboratory will be used for the logistic arrangements.

#### **5.4.2 Determination of drug concentration**

Samples for determination of ticagrelor and its active metabolite (AR-C124910XX) in plasma will be analysed by Covance on behalf of Clinical Bioanalysis Alliance AZ R&D, using an appropriate bioanalytical method. Full details of the analytical method used will be described in a separate bioanalytical report.

All samples still within the known stability of the analytes of interest (i.e., ticagrelor and its active metabolite), at the time of receipt by the bioanalytical laboratory, will be analysed.

#### **5.4.3 Storage and destruction of pharmacokinetic samples**

Pharmacokinetic (PK) samples will be disposed of after the Bioanalytical Report finalization or 6 months after issuance of the draft Bioanalytical Report (whichever is earlier), unless requested for future analyses.

PK samples may be disposed of or destroyed and anonymised by pooling. Additional analyses may be conducted on the anonymised, pooled PK samples to further evaluate and validate the analytical method. Any results from such analyses may be reported separately from the clinical study report (CSR).

Incurred sample reproducibility analysis, if any, will be performed alongside the bioanalysis of the test samples. The results from the evaluation will not be reported in the CSR but separately in a Bioanalytical Report. PK samples will be destroyed once CSR is finalized.

For each placebo subject, samples will only be analysed on a 'for cause' basis, e.g., if no quantifiable concentrations were observed in a subject's samples when the drug was expected to be present.

### **5.5 Pharmacodynamics**

#### **5.5.1 VerifyNow™ P2Y12 assay**

The VerifyNow™ P2Y12 test is a whole blood test used in the point-of-care setting to measure the level of platelet P2Y12 receptor blockade. Light transmittance increases as activated

platelets bind and aggregate fibrinogen-coated beads. The instrument measures this change in optical signal and reports results in PRU.

### **5.5.2 Collection of samples**

Blood samples for determination of PRU in whole blood will be taken at the time presented in [Table 1](#). The actual date and time will be collected in the eCRF. VerifyNow™ P2Y12 assay will be used. PRU values will be blinded to avoid any possible bias. At the end of the study PRU values will be unblinded and reconciled by an acceptable third party for analysis.

Samples will be collected and labelled as detailed in the Laboratory Manual.

## **5.6 Pharmacogenetics (Not Applicable)**

### **5.7 Biomarker analysis**

The patient's consent to the use of donated biological samples is optional.

Biological samples (e.g., plasma, serum samples) will be collected (see [Table 1](#) and [Section 5.8](#)) and may be analysed for exploratory biomarkers (sP-selectin, sCD40L and TXB2) to assess correlations with disease activity, effects of study drug, clinical outcomes and toxicity.

#### **5.7.1 Storage, re-use and destruction of biological samples**

Samples will be stored for a maximum of 15 years from the date of the Last Patient's Last Visit, after which they will be destroyed. The results of this biomarker research will be reported either in the CSR itself or as an addendum, or separately in a scientific report or publication. The results of this biomarker research may be pooled with biomarker data from other studies with the study drug to generate hypotheses to be tested in future research.

#### **5.7.2 Labelling and shipment of biological samples**

The Principal Investigator (PI) ensures that samples are labelled and shipped in accordance with the Laboratory Manual and the Biological Substance, Category B Regulations (materials containing or suspected to contain infectious substances that do not meet Category A criteria), see [Appendix C](#) 'IATA 6.2 Guidance Document'.

Any samples identified as Infectious Category A materials are not shipped and no further samples will be taken from the patient unless agreed with AZ and appropriate labelling, shipment and containment provisions are approved.

#### **5.7.3 Chain of custody of biological samples**

A full chain of custody is maintained for all samples throughout their lifecycle.

The PI at each centre keeps full traceability of collected biological samples from the patients while in storage at the centre until shipment or disposal (where appropriate) and keeps documentation of receipt of arrival.

The sample receiver keeps full traceability of the samples while in storage and during use until used or disposed of or until further shipment and keeps documentation of receipt of arrival.

AZ keeps oversight of the entire life cycle through internal procedures, monitoring of study sites and auditing of external laboratory providers.

Samples retained for further use are registered in the AZ Biobank during the entire life cycle.

#### **5.7.4 Withdrawal of Informed Consent for donated biological samples**

If a patient withdraws consent to the use of donated biological samples, the samples will be disposed of/destroyed, and the action documented. If samples are already analysed, AZ is not obliged to destroy the results of this research.

The Principal Investigator:

- Ensures patients' withdrawal of informed consent to the use of donated samples is notified immediately to AZ
- Ensures that biological samples from that patient, if stored at the study site, are immediately identified, disposed of /destroyed, and the action documented
- Ensures the laboratory(ies) holding the samples is/are informed about the withdrawn consent immediately and that samples are disposed of/destroyed, the action documented and the signed document returned to the study site
- Ensures that the patient and AZ are informed about the sample disposal.

AZ ensures the central laboratory(ies) holding the samples is/are informed about the withdrawn consent immediately and that samples are disposed of/destroyed and the action documented and returned to the study site.

